10.3. Enrollment Controls

Enrollment will remain open until one of the following events occurs:

- Approximately 10 patients are randomized
- The study is terminated at any time, at the Sponsor’s discretion.

Enrollment controls will be implemented per the Enrollment Communication Plan developed for this study.

11. Study Methods

11.1. Data Collection

The data collection schedule is shown in Table 11.1-1.

Procedure/ Assessment	Screening Period (duration >7 days)	Baseline Visit	Implant Procedure (standard of care)	Bipole Search Programming Visit and Period (post implant standard of care)	Randomization Visit (21±7 days post Bipole Search Visit)	Crossover Visit (21±5 days post Randomizati on Visit)	Release Visit (21±5 days post Crossover Visit)	Randomi zation Periods 1&2 (duration 21±5 days)	Long Term F/U Period (duration 90 ±14 days)	End of Study Visit (90 ±14 days post Release Visit)	Unscheduled Visit
Device Programming Report	-	-	-	X	X	X	X	-	-	X	X
Determine Preferred Program	-	-	-	-	-	-	X	-	-	-	-
Lead Fluoro Imaging (per center's standard of care)	-	-	X	-	-	-	-	-	-	-	X**
Randomization	-	-	-	-	X	-	-	-	-	-	-
Adverse event assessment	-	-	X	X	X	X	X	X	X	X	X

Abbreviations: AM – morning, PM - afternoon

* In the event that the unscheduled visit is an additional Device Procedure

** In the event that Investigator suspects lead migration, per standard of care

11.2. Study Candidate Screening

Patients will undergo screening during which their eligibility for the study will be determined. The screening will consist of collecting the baseline pain, medication and patient demographic information and determine suitability for SCS treatment.

11.3. Informed Consent

Written Informed Consent must be obtained for all patients who are potential study candidates. Patients will be asked to sign the Informed Consent form before any study-specific tests or procedures are performed. The context of the study must be fully explained to the patient in language that is easily understood by the patient. The patients must also be given the opportunity to ask questions and have those questions answered to their satisfaction.

The Informed Consent form is study specific and must be approved by the study Independent Ethics Committee (IEC).

Study personnel should explain that even if a patient agrees to participate in the study and signs an ICF, certain diagnostic or screening procedures might demonstrate that the patient is not eligible to continue participation (see Section 11.3.1).

11.3.1. Post-Consent Eligibility Validation

Baseline pain scores will be confirmed per inclusion criteria IC3 and IC4 during the screening period (and after patient had provided the written informed consent) and if they are not met, the patient will be withdrawn from study participation. The withdrawn patients will continue their treatment per center's standard of care.

11.4. Screening Period (duration >7 days within 90 days prior to Implant procedure) ending with Baseline visit

Visit type: period at home + office

Occurs after the patient has provided a written informed consent. The screening period lasts at least 7 days and should occur no more than 90 days prior to SCS Implant procedure. At the end of the screening period, during the Baseline visit it will be confirmed whether inclusion criteria are met.

Goal: Document pain scores and various quality of life measures to understand baseline pain condition and confirm eligibility of the patient.

11.5. Implant Procedure (Standard of Care)

Visit type: office

The SCS lead and system implant procedure will be done per center's standard of care but only those patients whose tight contact leads have contacts at or near the level overlying the T9/T10 intervertebral disc, as documented using standard of care imaging, will continue with

study participation. If this criterion is not satisfied they will be withdrawn and continue their treatment per center's standard of care.

11.6. Bipole Search Visit (after Implant procedure per center's standard of care when healing period complete, duration 2-4 weeks)

Visit type: office and home; regular contact with study patient is recommended

Goal: test paresthesia thresholds and distribution for selected programs, ensure that stimulation programs to be tested during bipole search are programmed into the device and study patient understands the use of the system and outcome reporting requirements in order to maximize efficiency of search. Measure the paresthesia thresholds and distribution for the bipole programs to be tested. Multiple programming visits may be done during this period (unscheduled).

11.7. Randomization Visit (21±7 days post Bipole Search Visit)

Visit type: office

Goal: collect information from bipole search, determine effective program(s), retest paresthesia thresholds and distribution for selected programs, ensure that stimulation programs to be tested during Randomization Period 1 are programmed into the device and study patient understands the use of the system and requirements in order to ensure appropriate stimulation testing during this period spent at home.

Important: Randomization will only occur for subjects who received adequate therapy from one or more configurations tested since the Bipole Search Visit. For subjects that did not receive adequate therapy, there will be no randomization but subject will be asked to be followed up until the End of Study Visit. Those subjects may be programmed according to site's standard of care.

11.8. Randomization Period 1 (duration of 21±5 days)

Visit type: home; regular contact with study patient is recommended

Goal: offer study patient opportunity to test, for each given stimulation program, a number of different amplitudes, each over a duration of several days, and report the outcomes.

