The Precision Spectra™ System includes an implantable 32-contact, multi-channel pulse stimulator (IPG) with a rechargeable power source. Periodically, the implant battery is recharged transcutaneously by a Precision™ radiofrequency charging unit. The stimulator can accept up to 4 leads and support a maximum of 32 contacts. The Precision Spectra™ System can be used with any commercially available Boston Scientific SCS leads.

A 32-contact Precision Spectra™ External Trial Stimulator (ETS) is used to provide trial stimulation through the surgically placed leads prior to implantation of the implantable stimulator. The leads are connected to the trial stimulator by means of the Precision Spectra™ OR Cable during the trial period, which may occur intraoperatively (on-the-table trial).

A Clinician Programmer (CP) is provided to facilitate communication with, and programming of, the IPG and ETS. A programming Wand is used to provide a link between the Clinician Programmer and the ETS/IPG.

A hand-held battery operated Precision Spectra™ Remote Control provides the patient with the ability to access basic stimulator functions.

The Precision Spectra™ System uses the standard surgical tools and accessories for facilitating lead insertion and placement.

Figure 5-1: Precision Spectra™ Products and Accessories

[figure not shown]
IPG	ETS	OR Cables	Remote Control	Clinician Programmer	Wand
		 2x8 OR Cable  1x16 OR			

Figure 5-2: Implantable Neurostimulator System

The Precision Spectra™ System delivers current-controlled, asymmetrical biphasic charge-balanced electrical pulses to each contact. Patients control the amplitude of stimulation and turn stimulation on or off via a wireless handheld remote control. The available stimulation parameters are as follows: frequency 2 to 1200 Hz, pulse width 20 to 1000 μ sec, and amplitude 0-25.5 mA with a 12.7 μ C pulse charge limit.

All of the devices used in this study are commercially approved in Europe.

6. Study Objectives

The objective of this study is to explore electrical field shape sensitivity and amplitude sensitivity in sub-perception SCS (anatomically-guided 1kHz stimulation) to obtain initial impressions of effect.

7. Study Endpoints

[figure not shown]
Collected data will be used to increase the understanding of the therapy, guide product development and help define the best practice for programming with 1kHz therapy.

- [REDACTED]
- | [REDACTED]
 - | [REDACTED]
 - | [REDACTED]
 - | [REDACTED]
 - | [REDACTED]

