8.2.1. Treatment and Control

This study compares two stimulation field types: bipolar vs DHM, both at 1 kHz. The cross-over study design allows for comparing these treatments using one of the stimulation types as an active control.

8.3. *Justification for the Study Design*

The study design is prospective, postmarket, exploratory, multi-center, randomized, double-blinded (subject, evaluator; programmer un-blinded) study to obtain initial impression on the sensitivity to electrical field shape and amplitude in 1kHz anatomically-guided subperception spinal cord stimulation for chronic neuropathic pain treatment. It is exploratory because little is known about the best electric field and amplitudes to optimize subperception SCS. Due to the nature of sub-perception SCS, blinding is possible and will contribute to the strength of the evidence gathered from this study. Randomization will allow for controlling for order effect as previous research in subperception SCS has shown that the order effect can dominate the treatment effect (Perruchoud et al., 2013).

9. Subject Selection

9.1. *Study Population and Eligibility*

The study will include patients until approximately 10 have entered the randomization phase. Patients will generally be recruited from physician's practice and will be eligible to receive 1 kHz Spinal Cord Stimulation therapy to treat their chronic neuropathic pain condition in the legs and back using the commercially-approved Boston Scientific's Precision Spectra™ System per local DFU.

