11.9. Crossover Visit (21±5 days post Randomization Visit)

Visit type: office

Goal: This is the crossover visit. The purpose is to collect information from Randomization Period 1, determine effective amplitude(s) and program(s), retest paresthesia thresholds and distribution for selected programs, ensure that stimulation programs to be tested during Randomization Period 2 are programmed into the device and study patient understands the use of the system and requirements in order to ensure appropriate stimulation testing during this period spent at home.

11.10. *Randomization Period 2 (duration 21±5 days)*

Visit type: home; regular contact with study patient is recommended

Goal: offer study patient opportunity to test, for each given stimulation program, a number of different amplitudes, each over a duration of several days and report the outcomes

11.11. *Release Visit (21±5 days post Crossover Visit)*

Visit type: office

Goal: collect information from Randomization Period 2, determine effective amplitude(s) and program(s), retest paresthesia thresholds and distribution for selected programs, ensure that stimulation programs to be tested during Long term Follow up are programmed into the device and study patient understands the use of the system and requirements in order to ensure appropriate stimulation testing during this period spent at home.

11.12. *Long Term Follow-up Period (duration approximately 90 days)*

Visit type: home; regular contact with study patient is recommended

Goal: Subject will be encouraged to keep their preferred program. Further therapy optimizations are allowed in this period (physician discretion). Multiple programming visits may be done during this period (unscheduled).

11.13. *End of Study Visit (90±14 days weeks post Release Visit for subjects who completed crossover phase or 90±14 days post Bipole Search Phase for subjects who did not respond to 1kHz Bipole Search)*

Visit type: office

Goal: collect information on the outcome and various quality of life measures during Long-term Follow-up and conclude study patient's participation in the study.

11.14. *Unscheduled Visit*

An unscheduled visit is any visit that occurs during patient's participation in the study that is not aforementioned.

Visit type: office

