Goal: There are many reasons for an unscheduled visit, which include (but not limited to) loss of therapy, suspected lead migration, need for additional reprogramming, need for addressing a complaint or potential adverse event. Information will be collected from the previous period as well as the reason for the unscheduled visit, retest paresthesia thresholds and distribution for selected programs, and to plan and explain patient's continuation in the study. If imaging is required per standard of care to address suspected lead migration, it may be performed at an unscheduled visit.

11.15. *Study Completion*

Each patient's participation in the study will be considered complete upon completion of the End of Study Visit or upon patient withdrawal.

Upon completing participation in the study patients will continue to be followed per center's standard of care practice.

11.16. *Source Documents*

Table 11.16-1 summarizes all source data requirements for this protocol. Where copies of the original source document as well as printouts of original electronic source documents are retained, these shall be signed and dated by a member of the investigational site team with a statement that it is a true reproduction of the original source document.

Table 11.16-1: Source Documentation Requirements

Requirement	Disposition
Hospital records or clinical and office charts including the evidence of but not limited to inclusion/exclusion criteria, informed consent, procedures, and assessment of adverse events	Retain at center
Clinical evaluations (eg. questionnaires, drawings)	Retain at center
Programming Pre and Post-visit Reports (program settings, impedance measurements, program usage, battery voltage etc)	Retain at center
Lead Fluoro Images (if done per center's standard of care)	Retain at center
Diary data	Retain at center

12. Statistical Considerations

12.1. *Endpoints*

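### The protocol gives each randomised setting both 15 days and 21±5 days, and its readable text controls the order of field types but not the order of amplitudes tested within a period

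*Protocol*

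**What the plan says.** **Period length.** The synopsis row on assigning patients to treatment and section 8.2 put each subject on one setting for 15 days and then on the other for 15 days. The synopsis follow-up schedule, the column heads of Table 11.1-1, and sections 11.8 to 11.11 give randomised periods and visit intervals of 21±5 days.

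**Amplitude.** Section 6 states the objective as to "explore electrical field shape sensitivity and amplitude sensitivity in sub-perception SCS". Section 7 says the data will "guide product development and help define the best practice for programming with 1kHz therapy". Section 11.8 describes Period 1 as follows: "Goal: offer study patient opportunity to test, for each given stimulation program, a number of different amplitudes, each over a duration of several days". Section 11.10 repeats this for Period 2: "each over a duration of several days and report the outcomes". The Crossover Visit (11.9) and the Release Visit (11.11) each use the period just ended to settle which amplitudes and programs were effective. Section 5 says of the device in general: "Patients control the amplitude of stimulation and turn stimulation on or off via a wireless handheld remote control".

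**Order control.** Sections 8.2 and 12.2.2 describe one randomisation, 1:1, to the two sequences of bipole and DHM. Section 8.3 gives the reason: "previous research in subperception SCS has shown that the order effect can dominate the treatment effect".

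**Records.** Table 11.16-1 lists programming reports made before and after visits (including program usage) and diary data. No readable text says that a diary day carries the amplitude in use.

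**The concern.** The two statements of period length cannot both hold. A subject who follows section 8.2 to the day falls outside the visit window of sections 11.9 and 11.11. Exposure to each field type, and the time available for amplitude testing, depend on which text a site follows.

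The amplitude question is a matter of design. Levels that each run for several days on one implanted system must be tested one after another. Section 8.3 treats order as a serious threat in sub-perception stimulation and randomises field type to deal with it. In the readable text, the other half of the objective has no such protection. If pain ratings drift within a period, or the next level is chosen from the response to the last, an apparent amplitude effect may be a time or selection effect. Later analysis can repair this only in part, and only if orders differ between subjects and the amplitude in use was recorded. At stake is how the first impressions of amplitude are read, and these are meant to inform programming practice.

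**Working it through.** **1. Period length (protocol figures only).**
- Window: 21 − 5 = 16 to 21 + 5 = 26 days. The 15-day figure lies 16 − 15 = 1 day below it, 21 − 15 = 6 days below the nominal length and 26 − 15 = 11 days below the upper end.
- Both periods together: 2 × 15 = 30 days, against 2 × 21 = 42 nominal (2 × 16 = 32 to 2 × 26 = 52).

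**2. Amplitude tests per period.** The protocol says only that each amplitude runs for several days, so d = 3, 4 or 5 days is an assumption. Tests = floor(T/d), shared over all programs tested in the period:

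| T (days) | d = 3 | d = 4 | d = 5 |
|---|---|---|---|
| 15 | 5 | 3 | 3 |
| 16 | 5 | 4 | 3 |
| 21 | 7 | 5 | 4 |
| 26 | 8 | 6 | 5 |

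**3. Does randomising field type protect amplitude?** No. If amplitudes follow a common order within a period, the link between amplitude and time is the same in the bipole-first and DHM-first sequences.

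**4. Size, as illustration only.** The protocol gives no drift, number of levels or days per level. Assumed: one program, 3 levels of 5 days (which fits 15 days), no true amplitude effect, and a linear drift g of 0.05 points per day on a 0–10 scale (range 0.02 to 0.10).

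Spurious difference between two levels = (difference in block position) × 5 × g.
- Common rising order, lowest to highest: 2 × 5 × 0.05 = 0.50 (0.20 at 0.02; 1.00 at 0.10).
- Common but not monotone order, for example lowest, highest, middle: highest minus lowest is 1 × 5 × 0.05 = 0.25, and middle minus lowest is 2 × 5 × 0.05 = 0.50. Each level still occupies one block in every subject, so level and time block cannot be separated. Any common order does this.
- Rising order in a share p of sequences and falling in the rest: (2p − 1) × 0.50, so 0.25 at p = 0.75 and 0 at p = 0.5.
- No drift: 0.
- Random order: over the 6 permutations, highest-minus-lowest position has mean 0 and SD √2 = 1.414. Per sequence this is 1.414 × 5 × 0.05 = 0.354. Over about 10 subjects × 2 periods = 20 sequences, 0.354/√20 = 0.079 from drift alone (0.032 at 0.02; 0.158 at 0.10).

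A simulation with 3 to 5 levels of 3 to 7 days (some of which fit 21 days but not 15), 10 subjects, 2 periods and an assumed residual SD of 1 agrees. An ascending order gave spurious differences of about 0.2–0.3, 0.5–0.8 and 1.0–1.6 points at the three drifts. Randomised order gave values within ±0.01 of zero.

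**5. What random order does not remove.** Take true effects of 0, 0.5 and 1.0, and let day 1 of each later 5-day block still show the previous level. Over the 6 orders the observed highest-minus-lowest difference is 0.9, 0.8, 0.7, 0.7, 0.8 and 0.9, mean 0.80 against a true 1.0. Without the day-1 ratings it is 1.00, provided carry-over lasts no more than one day.

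**The case against.** The strongest reply on amplitude is that this argues from silence in a document with large unreadable parts. Figure 8-1, the endpoint list, most of Table 11.1-1 and a block after section 12.1.4 cannot be read. The key to Table 11.1-1 explains morning and afternoon entries that no readable row contains, so rows have clearly gone, plausibly including diary ratings. Sections 11.8 and 11.10 state goals, not procedures. Sections 11.7 and 11.9 say the patient must understand the requirements for stimulation testing, which suggests instructions exist. Section 5 describes the commercial device and does not show that study patients choose their own order. Section 8.3 concerns the order of treatments, and nothing in the protocol demonstrates an order effect for amplitude. A response-guided search is also a reasonable way to "determine effective amplitude(s) and program(s").

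Most of this stands, and it is why the point is conditional. A reader might infer that the protocol has no amplitude scheme, or that amplitude is wholly confounded with time. The documents support neither: a scheme may sit in the unreadable parts, and the order actually used is not stated. What survives is that the readable assignment, justification and bias-control sections address order for field type only, and that sections 11.8 and 11.10 point to no scheme.

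On period length, one could say that 15 days is the active part of a 21-day interval. No readable text says so or accounts for the remaining 1 to 11 days, and sections 11.8 and 11.10 give 21±5 days as the duration of the randomised period itself.

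**Conclusion.** **Period length: wrong as written.** The 15-day and 21±5-day statements contradict each other, with 15 lying 1 day outside the window and 6 days below its centre. This rests on the protocol's own figures. A reader might go on to infer which figure is the error; the document does not settle that.

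**Amplitude order: a cheap improvement, conditional on the unreadable parts.** On the readable text, amplitude may be confounded with time in the period or with earlier response: fully if all subjects share any common order, partly otherwise. Under the assumptions above the spurious difference runs from 0 to 1.00 point for three 5-day levels. Nothing in the protocol places the trial within that range. A reader might also infer that the study's results are invalid. They are not: about 10 subjects are randomised, there are no hypotheses and the statistics are descriptive, so no test is affected. Only the interpretation of the amplitude impressions is limited.

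**What to change.** 1. Reconcile the 15-day and 21±5-day statements across the synopsis, section 8.2, Table 11.1-1 and sections 11.8 to 11.11. If they describe different things, say what each covers. No length is proposed here.
2. If an amplitude scheme already exists in a part not readable here, cross-refer to it from sections 11.8 and 11.10. Otherwise state there that the order of whichever levels are selected for testing is randomised or counterbalanced across subjects and periods, and that the amplitude in use is recorded for each diary day. Daily recording would also let results be described with and without ratings taken just after a change, since random order leaves carry-over in place.
3. If the order must stay response-guided, record it and describe the amplitude results as not controlled for time.

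None of this sets a level, a limit or a duration.

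**Cost.** An order list per subject and period, one diary item and patient instruction; no extra subjects. An assigned order relies on patients following it on the remote control, and some may need extra contact or reprogramming. It also restricts response-guided searching in the two periods. The bipole search does not replace this for DHM, because section 11.6 describes testing bipole programs only. Further optimisation under section 11.12 comes only after the Release Visit has settled the effective amplitudes and the preferred program. Option 3 avoids that restriction, at the price of a weaker reading of amplitude.

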11.9. Crossover Visit (21±5 days post Randomization Visit)

Visit type: office

Goal: This is the crossover visit. The purpose is to collect information from Randomization Period 1, determine effective amplitude(s) and program(s), retest paresthesia thresholds and distribution for selected programs, ensure that stimulation programs to be tested during Randomization Period 2 are programmed into the device and study patient understands the use of the system and requirements in order to ensure appropriate stimulation testing during this period spent at home.

11.10. *Randomization Period 2 (duration 21±5 days)*

Visit type: home; regular contact with study patient is recommended

Goal: offer study patient opportunity to test, for each given stimulation program, a number of different amplitudes, each over a duration of several days and report the outcomes

11.11. *Release Visit (21±5 days post Crossover Visit)*

Visit type: office

Goal: collect information from Randomization Period 2, determine effective amplitude(s) and program(s), retest paresthesia thresholds and distribution for selected programs, ensure that stimulation programs to be tested during Long term Follow up are programmed into the device and study patient understands the use of the system and requirements in order to ensure appropriate stimulation testing during this period spent at home.

11.12. *Long Term Follow-up Period (duration approximately 90 days)*

Visit type: home; regular contact with study patient is recommended

Goal: Subject will be encouraged to keep their preferred program. Further therapy optimizations are allowed in this period (physician discretion). Multiple programming visits may be done during this period (unscheduled).

11.13. *End of Study Visit (90±14 days weeks post Release Visit for subjects who completed crossover phase or 90±14 days post Bipole Search Phase for subjects who did not respond to 1kHz Bipole Search)*

Visit type: office

Goal: collect information on the outcome and various quality of life measures during Long-term Follow-up and conclude study patient's participation in the study.

11.14. *Unscheduled Visit*

An unscheduled visit is any visit that occurs during patient's participation in the study that is not aforementioned.

Visit type: office

Goal: There are many reasons for an unscheduled visit, which include (but not limited to) loss of therapy, suspected lead migration, need for additional reprogramming, need for addressing a complaint or potential adverse event. Information will be collected from the previous period as well as the reason for the unscheduled visit, retest paresthesia thresholds and distribution for selected programs, and to plan and explain patient's continuation in the study. If imaging is required per standard of care to address suspected lead migration, it may be performed at an unscheduled visit.

11.15. *Study Completion*

Each patient's participation in the study will be considered complete upon completion of the End of Study Visit or upon patient withdrawal.

Upon completing participation in the study patients will continue to be followed per center's standard of care practice.

11.16. *Source Documents*

Table 11.16-1 summarizes all source data requirements for this protocol. Where copies of the original source document as well as printouts of original electronic source documents are retained, these shall be signed and dated by a member of the investigational site team with a statement that it is a true reproduction of the original source document.

Table 11.16-1: Source Documentation Requirements

Requirement	Disposition
Hospital records or clinical and office charts including the evidence of but not limited to inclusion/exclusion criteria, informed consent, procedures, and assessment of adverse events	Retain at center
Clinical evaluations (eg. questionnaires, drawings)	Retain at center
Programming Pre and Post-visit Reports (program settings, impedance measurements, program usage, battery voltage etc)	Retain at center
Lead Fluoro Images (if done per center's standard of care)	Retain at center
Diary data	Retain at center

12. Statistical Considerations

12.1. *Endpoints*

